#### Dose adjustment during the study

Patients who, during the course of the study, develop renal impairment (Estimated GFR ≤50 mL/min on 2 consecutive tests at least 1 week apart) will have their dose adjusted to 2.5 mg saxagliptin or matching placebo. Once reduced to 2.5 mg saxagliptin or placebo, there will be no further dose-adjustment even if the estimated GFR subsequently increased sufficiently to meet initial requirements for the 5 mg saxagliptin or placebo dosing regimen. The IVRS/IWRS will be used to allocate the adjusted IP.

#### 5.5.3 Labelling

Packing and labelling of the IP will be carried out by AstraZeneca or the CRO in accordance with current Good Manufacturing Practices (GMPs). The labels will be prepared in accordance with GMP and local regulatory guidelines. The labels will fulfil GMP Annex 13 requirements for labelling and will be translated into the local language. Booklet labels or single panel labels will be used.

#### 5.5.4 Storage

All IP should be kept in a secure place under appropriate storage conditions. The IP label on the bottle specifies the appropriate storage.

# 5.6 Concomitant and post-study treatment(s)

Background medication and post-study treatment will not be provided by the Sponsor.

## 5.6.1 Prohibited medication

Treatment with DPP4 inhibitors or GLP-1 mimetics is not allowed for the duration of the study and within 6 months of the start of the study.

#### 5.6.2 Use with medications known to cause hypoglycaemia

Insulin secretagogues, such as sulphonylureas, cause hypoglycaemia. Therefore, a lower dose of the insulin secretagogue or injectible insulin may be required to reduce the risk of hypoglycaemia when used in combination with saxagliptin.

#### 5.6.3 Other medication

Patients are eligible, at the Investigator's discretion and based on local treatment guidelines, for adjustments in their antidiabetic treatment. This includes discontinuing or changing the dose of their concomitant antidiabetic medication as well as adding other antidiabetic treatments. All patients will be treated to regional standards of care for cardiovascular risk factors (eg, blood pressure, lipids) and HbA1c. Investigators will be duly informed of this requirement via study aids and via information provided at Investigator's Meetings. However, the medications for other medical conditions are allowed based on the current local saxagliptin label. Regardless of the need for a change in concomitant medication, patients will remain on the randomised study medications unless specifically meeting criteria for discontinuation of IP.

Other medication, which is considered necessary for the patient's safety and well-being, may be given at the discretion of the Investigator.

Recording of concomitant medication with a duration of  $\geq 3$  months in the appropriate sections of the Case Report Form (CRF) will be according to type of medication:

- Glucose-lowering drugs including injectables (insulin) by drug category or generic drug. Dose and dose step increase of ≥1 step for oral antidiabetics and ≥25% for insulin to be recorded if the dose regimen lasts at least 3 months
- CV medications including angiotensin-converting enzyme inhibitors and angiotensin-receptor blockers by drug category
- All other medication by drug category only, with no collection of start/stop dates

# 5.7 Treatment compliance

The administration of all medication (including IPs and other medication) should be recorded in the appropriate sections of the CRF.

Patients will be instructed to return all unused IP and any empty packages at each study visit. Compliance will be discussed at each study visit and assessed based on returned IP as follows, the Investigator will make a subjective judgement of the compliance based on 2 categories ("good":  $\leq 20\%$  deviation from expected number of tablets; and "questionable": >20% deviation). If compliance is "questionable", the Investigator should counsel or instruct the patient on the importance of taking his/her IP as prescribed.

# 5.7.1 Accountability

The study drug provided for this study will be used only as directed in the study protocol.

The study personnel will account for all IP drugs dispensed to and returned from the patient.

AstraZeneca or its representative will oversee that study personnel account for IPs received at the study centre, unused IP and IP for appropriate destruction. At the termination of the study or at the request of AstraZeneca or its designee, the Investigator must return any unused supplies to AstraZeneca or its representative. Certificates of delivery, destruction and return should be signed.

# 5.8 Discontinuation of investigational product

Patients may be discontinued from IP in the following situations:

- Voluntary discontinuation by the patient who is at any time free to discontinue treatment, without prejudice to further treatment
- Safety reasons as judged by the Investigator, by AstraZeneca, BMS and/or a representative.

Study-specific discontinuation criteria are listed below:

- Increase of ALT and/or AST >3 times the upper limit of normal (ULN) **and** increase of TB >1.5 times ULN confirmed at a repeated measurement within 4 days
- Increase of ALT or AST >10 times ULN confirmed at a repeated measurement within 4 days
- Pregnancy (discontinue IP and notify AstraZeneca or its representative), see Section 13.3

Cases where patients are incorrectly randomised (ie, the patient does not meet the required inclusion/exclusion criteria for the study), should be discussed with TIMI Study Group representative prior to any actions being taken (see Section 5.3).

# 5.8.1 Procedures for discontinuation of a patient from investigational product

Patients who are discontinued from IP should always be asked to continue in the study until the closing of the study.

A patient who decides, and/or is recommended by treating physician to discontinue IP, will always be asked about the reason(s) and the presence of any AEs. If possible (all efforts taken), the patient will be seen and assessed by an Investigator(s) and as scheduled for other patients preferably complete all assessments of the EoT/ Closing Visit. AEs will be followed up (See Section 6.4.3) and IP should be returned by the patient. Following EoT assessments the patient should be followed for **AEs and** clinical events at the scheduled visits until the study end. The Closing Visit should preferably be a visit to the site.

Alternatively, if the patient does not agree to this option, a modified follow up through regular telephone contacts or a contact at study closure should be arranged, if agreed to by the patient and in compliance with local data privacy laws/practices.

## **Restart of IP**

Whenever possible restart of IP should be encouraged. Even if a premature EoT visit was completed due to the discontinuation of IP, this should not prevent complete study follow-up procedures including the final EoT/Closing Visit, following restart of randomised treatment.

If a patient is withdrawn from the study, see Section 5.9.

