# 4.2 Exclusion criteria

Patients should not enter the study if any of the following exclusion criteria are fulfilled:

- 1. Any conditions that, in the opinion of the Investigator, may render the patient unable to complete the study including non-CV disease (eg, active malignancy, cardiomyopathy, cirrhosis, or chronic lung disease) with a likely fatal outcome within 5 years
- 2. Current or previous (within 6 months) treatment with an incretin-based therapy such as DPP4 inhibitors and or GLP-1 mimetics
- 3. Acute vascular (cardiac or stroke) event <2 months prior to randomisation
- 4. Initiation of chronic dialysis and/or renal transplant and/or a serum creatinine >6.0 mg/dL
- 5. Pregnant or breast-feeding patients
- 6. History of human immunodeficiency virus
- 7. Patients being treated for severe auto immune diseases such as lupus
- 8. Any patient currently receiving chronic (>30 consecutive days) treatment with an oral steroid
- 9. Patients with:
  - Body mass index  $>50 \text{ kg/m}^2$
  - Last measured HbA1c  $\geq$ 12%
  - Sustained BP >180/100 mm Hg
  - LDL-C >250 mg/dL (> 6.48 mmol/L) (based on the last measured and documented laboratory measurement in the previous 6 months)
  - Triglycerides >1000 mg/dL (>11.3 mmol/L) (based on the last measured and documented laboratory measurement in the previous 6 months)
  - HDL-C <25 mg/dL (<0.64 mmol/L) (based on the last measured and documented laboratory measurement in the previous 6 months)
  - Known liver function tests >3 times upper limit of normal (ULN), (based on the last measured and documented laboratory measurement in the previous 6 months)
- 10. Involvement in the planning and/or conduct of the study (applies to both AstraZeneca and BMS or representative staff and/or staff at the study site)
- 11. Previous randomisation in the present study
- 12. Participation in another clinical study with IP and/or intervention within 30 days prior to Visit 1
- 13. Individuals at risk for poor protocol or medication compliance

For procedures for withdrawal of incorrectly randomised patients, see Section 5.3.

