# 5.3 Procedures for handling patients incorrectly enrolled or randomised or initiated on investigational product

**Patients who fail to meet the inclusion/exclusion criteria** should not, under any circumstances, be enrolled or randomised. There can be no exceptions to this rule.

When patients who do not meet the eligibility criteria are randomised in error or incorrectly started on treatment, or when patients subsequently fail to meet the study criteria post-initiation, a discussion should occur between the TIMI Study Group representative and the Investigator regarding whether to continue or discontinue the patient from treatment.

The TIMI Study Group representative is to ensure all such decisions are appropriately documented. In situations where an agreement cannot be reached, the patient's study therapy should be stopped.

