## Unscheduled laboratory assessments

- If ALT and/or AST >3 times ULN **and** increase of TB >1.5 times ULN, a repeated measurement should be done within 4 days. If the increase is confirmed, the patient should be discontinued from IP. Similarly, an increase of ALT or AST >10 times ULN confirmed at a repeated measurement within 3 to 4 days should lead to discontinuation of IP (see Section 5.8).
- If an estimated GFR  $\leq$ 50 mL/min, a repeated measurement should be done after 1 week. If the repeat value is still  $\leq$ 50 mL/min, then the patient should be assigned 2.5 mg or matching placebo via the IVRS/IWRS. The estimated GFR will be calculated from serum creatinine according to MDRD, (see Section 11.2.1).

- For cases of suspected pancreatitis, serum lipase analysis should be performed at the central laboratory, if possible; otherwise, the local laboratory values of serum lipase and/or amylase should be recorded.
- When clinically indicated, such as in settings of unusual or prolonged infections, lymphocyte counts should be measured.

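### Section 5.8.1 encourages restart of study drug without excepting patients stopped for a confirmed liver criterion, at odds with the sponsor's position on rechallenge in Appendix B

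*Protocol*

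**What the plan says.** Section 5.8 lists three study-specific reasons to stop study drug: two liver criteria and pregnancy. The first liver criterion is ALT and/or AST above 3 times ULN together with total bilirubin above 1.5 times ULN, confirmed on repeat. The second is "Increase of ALT or AST >10 times ULN confirmed at a repeated measurement within 4 days". The section also allows a stop on general grounds: "Safety reasons as judged by the Investigator, by AstraZeneca, BMS and/or a representative".

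Section 6.4.5, under unscheduled laboratory assessments, repeats the action for the first criterion ("If the increase is confirmed, the patient should be discontinued from IP") and says the same of the second.

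The paragraph on restart in Section 5.8.1 then says "Whenever possible restart of IP should be encouraged". The rest of that paragraph is administrative: having completed a premature end-of-treatment visit does not prevent full follow-up once treatment has resumed.

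Appendix B, in its list of factors for judging causality, remarks under rechallenge experience that the sponsor would not normally advise or back re-exposure.

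**The concern.** The encouragement to restart sits in the subsection that governs every discontinuation, including the hepatic ones, and it is not limited to voluntary or temporary stops. A site that follows it literally is steered towards re-exposing a patient who has had a confirmed liver signal on study drug. The protocol gives no level to which the tests must fall and names no one to consult first. A site that also reads Appendix B finds guidance pointing the other way, with nothing to say which prevails.

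What is at stake is the safety of individual patients. The trial's inference is not at stake.

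**Working it through.** The plan gives no figure to reproduce. The check is to set the relevant texts side by side and ask whether any of them closes the gap.

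**1. Is the liver stop permanent?** Sections 5.8 and 6.4.5 say that drug is discontinued. Neither says for how long.

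**2. Is restart conditional?** Section 5.8.1 gives no condition. Section 6.2.1 mentions interrupted and restarted drug only to say which visits the patient attends. The discussion with the TIMI Study Group representative in Section 5.3 is "regarding whether to continue or discontinue the patient from treatment"; it does not mention restart. For the renal trigger, Section 5.5.2 does state what follows recovery: "there will be no further dose-adjustment even if the estimated GFR subsequently increased". That rule concerns dose level in patients who stay on drug, so it is only a loose parallel, but it shows that the protocol spells out the consequence of recovery for one laboratory trigger and not for the other.

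**3. Would recovery be documented anyway?** Section 3.1 places the end-of-treatment assessments, which include ALT, AST and total bilirubin, at the time of discontinuation where possible. That panel would describe the abnormality, not its resolution. At later visits off drug, Section 3.1 asks only for adverse events and suspected clinical events. Adverse events are followed up (Section 5.8.1) and unscheduled laboratory visits are allowed (Section 3.1), but no liver test is required before restart. After restart the patient returns to Table 3, where the liver panel falls at months 12, 24, 36 and 48 and at end of treatment. The spacing is 24 − 12 = 12 months, so up to about 12 months could pass before the next scheduled test, depending on when restart falls.

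**4. Does expedited reporting catch these patients?** Section 6.4.2 puts AST or ALT of at least 3 times ULN, with total bilirubin above 2 times ULN or jaundice, on serious-event timelines. Section 6.4.4 brings such cases to TIMI no later than the end of the next business day. In multiples of ULN:

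| Stop criterion met | Reached by this reporting rule? |
|---|---|
| First, bilirubin > 2, or jaundice | Yes |
| First, bilirubin > 1.5 to 2, no jaundice | No, unless serious for another reason |
| Second, bilirubin > 2, or jaundice | Yes |
| Second, bilirubin ≤ 2, no jaundice | No, unless serious for another reason |

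Where the rule applies, it is a reporting step and not an approval to restart.

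**5. What levels could a restarted patient have?** Neither stop criterion is met when ALT and AST are at most 10 and, in addition, either both are at most 3 or bilirubin is at most 1.5. The part of this region above the Section 4.2 entry limit of 3 is transaminases above 3 and up to 10 with bilirubin at most 1.5. Its upper edge is 10 / 3 = 3.3 times the entry limit. This region comes from the stop thresholds and is open equally to patients who never stopped. It shows only that falling back below a stop threshold is not the same as having resolved, so a restart condition needs its own level.

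**The case against.** The strongest reply is that the restart sentence is a general retention statement, to be read subject to the specific stop rules. Pregnancy is not excepted either, yet nobody would restart a pregnant patient on the strength of it. Section 5.6.3 likewise keeps patients on drug only while they do not meet a discontinuation criterion. This carries weight, and most investigators would probably read it so. The pregnancy comparison is incomplete, however. During pregnancy the reason for stopping is still present, whereas a liver signal can fade, and that is when the restart sentence starts to operate.

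Second, there are safeguards. Restart is nowhere mandated, and Section 5.8 lets the investigator or the sponsors stop drug on safety grounds. Section 6.4.3 makes a laboratory change that causes discontinuation a reportable adverse event, whose causality assessment leads to Appendix B. Many of the graver cases reach TIMI quickly. All of this stands and keeps the point minor. None of it sets a condition for restart.

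Third, detailed procedures are assigned to the project operational manual (Section 12.5.2) and overall risk and benefit to the Investigator's Brochure or package leaflet (Section 1.4). A restart condition may exist there and cannot be checked. The unqualified encouragement is still in the protocol itself.

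A reader might infer that encouragement to restart is the only written guidance on re-exposure. Appendix B shows otherwise. A reader might also infer that the protocol invites restart after a trivial fall in ALT or bilirubin. The documents do not describe that: drug is returned on discontinuation and issued at regular site visits six months apart.

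**Conclusion.** The point holds as a minor patient-safety improvement. Read literally, Section 5.8.1 favours re-exposure after a confirmed liver stop, and it conflicts with the sponsor's stated position in Appendix B. That makes it more than missing detail. It would go too far to say that the protocol requires rechallenge after liver injury: it fails to exclude or condition it.

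Two of the three study-specific stop criteria are hepatic and neither is excepted. The protocol gives no frequency of liver stops or restarts, so the number of patients is unknown; that it is small is an assumption. Patients off drug are asked to stay in follow-up, and all randomised patients are analysed as randomised, so alpha, power and the primary estimate are unaffected. The conclusion assumes that no document outside the protocol already sets a restart condition.

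**What to change.** Add to the restart paragraph of Section 5.8.1: the encouragement to restart does not apply to patients discontinued for a confirmed liver criterion in Section 5.8; such patients may restart, if at all, only after repeat testing documents resolution (ALT and AST at or below 3 times ULN and total bilirubin at or below 1.5 times ULN) and after discussion with the TIMI Study Group representative.

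The levels reuse the protocol's own thresholds: 3 times ULN is the entry limit in Section 4.2, and 1.5 times ULN is the bilirubin limit in the first stop criterion. Their use as restart levels is a proposal that the clinical team may tighten. The contact already exists in Section 5.3.

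The cost is one sentence, a repeat liver panel in the few patients considered for restart, and slightly fewer or later restarts among them. They remain in follow-up and in the intention-to-treat population.

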# 5.9 Withdrawal from study

Patients are at any time free to withdraw from the study (IP and assessments), without prejudice to further treatment (withdrawal of consent). Such patients will always be asked about the reason(s) and the presence of any AEs. If possible, they will be seen and assessed by an Investigator. AEs will be followed up (see Section 6.4.3). IP should be returned by the patient.

Survival, based on publicly available sources, will be investigated at the scheduled study end and in cases where patients have withdrawn consent.

To prevent patients being lost to follow-up, their contact details, including next of kin contacts should be collected initially and updated regularly by the site staff or representative.

# 6. COLLECTION OF STUDY VARIABLES

# 6.1 Recording of data

A Web-Based Data Capture (WBDC) system will be used for data collection and query handling. The Investigator will ensure that data are recorded on the CRF as specified in the study protocol and in accordance with the instructions provided.

The Investigator will sign the completed CRF. A copy of the completed CRF will be archived at the study site.

All suspected events included in the composite endpoint of CV death, non-fatal MI, or non-fatal ischaemic stroke and secondary CV endpoints will be recorded in the respective

appropriate modules of the CRF. Investigators are also required to provide the CEC copies of source documents, eg, medical records (discharge summary, death certificate, autopsy report, etc). Refer to the *Investigator Manual for Events to be Adjudicated* which will be available at study start.

# 6.2 Data collection and enrolment

The following data will be collected at enrolment and recorded in the appropriate sections of the CRF (see Table 3).

- Date of signed informed consent
- Inclusion and exclusion criteria
- Demography: Date of birth, gender, race, and geographic region
- Pregnancy test at entry (excluding females postmenopausal  $\geq 2$  years)
- Fasting blood sampling for laboratory assessments of HbA1c, FPG, insulin, CBC with differential, serum creatinine, TB, ALT and AST, and limited urinalysis for assessment of albumin and creatinine (central laboratory)
- Medical history information including number of years of T2DM, previous history of CV disease and CV risk factors
- Physical examination including vital signs (BP and pulse), height, weight, waist circumference, and 12-lead ECG
- Prior and concomitant medication:
  - Glucose-lowering drugs including injectables (insulin) by drug category or generic drug. Dose and dose step increase of ≥1 step for oral antidiabetics and ≥25% for insulin to be recorded if the dose regimen lasts at least 3 months
  - CV medications including angiotensin-converting enzyme inhibitors and angiotensin-receptor blockers by drug category, where the treatment lasts at least 3 months
  - All other medication by drug category only, with no collection of start/stop dates, where the treatment lasts at least 3 months
- PRO questionnaire: the EQ-5D (in countries with validated translation available)
- Diet and lifestyle advice

- Optional: Date of signed addendum of the ICF for blood sampling for biological research.
- Optional: Date of signed addendum of the ICF for blood sampling for genetic researching.

#### 6.2.1 Follow-up procedures

Randomised patients who discontinue randomised treatment prematurely should complete the procedures described for EoT/Closing Visit at the time of the discontinuation of IP. Following discontinuation of treatment, these patients should attend the remaining study visits or will be contacted by phone to have AEs and suspected clinical events recorded until the end of the study. The Closing Visit should preferably be a visit at the site.

Patients on randomised treatment, also where IP was interrupted and restarted, should attend all remaining visits for assessments, procedures, and provision of IP (according to Table 3) until the end of the study.

The blood sample for pharmacogenetic research may be drawn after Visit 1 if needed, provided written informed consent is given, see Appendix F.

Diet and lifestyle advice will be provided at each visit. The following assessments will be done at the follow-up visits:

- Telephone contact every 3rd month (ie, between clinic visits):
  - Recording of AEs
  - Recording of clinical events (applicable also to patients who prematurely stopped randomised treatment)
  - Recording of use of IP
  - Recording of concomitant medication.
- Visits 2, 4, 6, 8 and 10 (6, 18, 30, 42 and 54 months):
  - Recording of AEs (applicable also to patients who prematurely stopped randomised treatment)
  - Recording of clinical events (applicable also to patients who prematurely stopped randomised treatment)
  - Pregnancy test (excluding females postmenopausal  $\geq 2$  years)
  - Return of IP and assessment of compliance

- Dispensing of new IP
- Recording of concomitant medication
- If any event included in the composite endpoint of CV death, non-fatal MI or non-fatal ischaemic stroke has occurred, the EQ 5D will be completed
- Visits 3 and 7 (12 and 36 months):
  - Recording of AEs (applicable also to patients who prematurely stopped randomised treatment)
  - Recording of clinical events (applicable also to patients who prematurely stopped randomised treatment)
  - Pregnancy test (excluding females postmenopausal  $\geq 2$  years)
  - Return of IP and assessment of compliance
  - Dispensing of new IP
  - Recording of concomitant medication
  - Non-fasting blood sampling for assessments of HbA1c, CBC with differential, serum creatinine, TB, ALT and AST (central laboratory)
  - Limited urinalysis for assessment of albumin and creatinine (central laboratory)
  - Targeted physical examination as well as vital signs: weight, BP and pulse
  - PRO questionnaire: the EQ-5D (in countries with validated translation available)
- Visit 5 (24 months):
  - Recording of AEs (applicable also to patients who prematurely stopped randomised treatment)
  - Recording of clinical events (applicable also to patients who prematurely stopped randomised treatment)
  - Pregnancy test (excluding females postmenopausal  $\geq 2$  years)
  - Return of IP and assessment of compliance
  - Dispensing of new IP

- Recording of concomitant medication
- Fasting blood sampling for laboratory assessments of HbA1c, FPG, insulin, lipids (Total-Cholesterol, LDL-Cholesterol, HDL-Cholesterol and TG), CBC with differential, serum creatinine, TB, ALT and AST, and limited urinalysis for assessment of albumin and creatinine (central laboratory)
- Targeted physical examination as well as vital signs: weight, waist circumference, BP and pulse
- PRO questionnaire: the EQ-5D (in countries with validated translation available)
- Optional blood sample for biological research.
- Visit 9 (48 months):
  - Recording of AEs (applicable also to patients who prematurely stopped randomised treatment)
  - Recording of clinical events (applicable also to patients who prematurely stopped randomised treatment)
  - Pregnancy test (excluding females postmenopausal  $\geq 2$  years)
  - Return of IP and assessment of compliance
  - Dispensing of new IP
  - Recording of concomitant medication
  - Non-fasting blood sampling for assessment of HbA1c, haematology and CBC with differential, serum creatinine, TB, ALT and AST, and limited urinalysis for assessment of albumin and creatinine (central laboratory)
  - Targeted physical examination as well as vital signs: weight, BP and pulse
  - PRO questionnaire: the EQ-5D (in countries with validated translation available)
- End of Treatment/ Closing Visit:
  - Recording of AEs (applicable also to patients who prematurely stopped randomised treatment)

- Recording of clinical events (applicable also to patients who prematurely stopped randomised treatment)
- Pregnancy test (excluding females postmenopausal  $\geq 2$  years)
- Return of IP and assessment of compliance
- Recording of concomitant medication
- Fasting blood sampling for laboratory assessments of HbA1c, FPG, insulin, lipids (Total-Cholesterol, LDL-Cholesterol, HDL-Cholesterol and TG), CBC with differential, serum creatinine, TB, ALT and AST, and limited urinalysis for assessment of albumin and creatinine (central laboratory)
- Targeted physical examination as well as vital signs: weight, waist circumference, BP and pulse
- PRO questionnaire: the EQ-5D (in countries with validated translation available).

